## 5.2 Withdrawal of Patients

Patients will be discontinued from the Treatment Phase and enter the Follow-up Phase for assessment of efficacy endpoints under the following circumstances:

- Completion of Treatment Phase
- Persistent disease: lack of a response to treatment
- Relapsed disease: re-appearance of disease following CR, CRp, or CRI
- Unacceptable toxicity
- Patient non-compliance with protocol
- Administration of non-protocol chemotherapy
- Concurrent illness which, in the judgment of the investigator, effects assessment of clinical status to a significant degree, and requires discontinuation of protocol therapy.

Any adverse event that, in the judgement of the investigator, may cause severe or permanent harm if the study intervention is continued will result in subject discontinuation from the study. Any treatment related grade 3 or higher non-hematological toxicity that does not resolve to grade 2 within 14 days of receiving treatment for the event will result in subject discontinuation from the study.

During any phase of the study, if a patient requests to stop treatment and/or follow-up, the patient will be discontinued and no further information will be collected. The patient will be classified as withdrawal of consent.

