## 4.4 Repeat of Induction

Patients achieving aplasia/hypoplasia (<5% blast count) will not receive second inductions. Patients with reduced tumor burden and evidence of persistent leukemia who remain fit for additional intensive chemotherapy can be given second inductions up to 60 days (measured from day 1 of chemotherapy treatment) after the first induction treatment date.

Patients unable to achieve a response (CR, CRp, or CRi) after up to 2 inductions are discontinued from further treatment and followed for survival.

Dosing for second induction:

- CPX-351 at 100 u/m^2 will be administered on days 1 and 3

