#### 4.6 Follow-up Phase

Patients will be followed at monthly intervals or more frequently depending on clinical circumstances until start of the next salvage treatment, death or for 1 year from date of enrollment. Patients alive and in remission after 1 year will be followed annually or more frequently depending on clinical circumstances for up to 5 years from enrollment. For EFS evaluation, events include: documentation of persistent AML after induction, relapse after achievement of CR/CRp/ CRi, or death. Bone marrow assessments will be performed at any time during follow up when recurrent cytopenias raise the suspicion of AML relapse. After documentation of persistent leukemia or relapse, follow-up for OS will continue. At the start of HSCT or non-protocol AML treatment of any sort or 30-days following the last dose, whichever occurs first, AE data collection will stop.

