### 6.3 Early Termination or End of Treatment Phase

Any patient that completes or discontinues treatment must have the following evaluations performed within 30 days after termination and prior to the initiation of any salvage therapy, if not performed within the last 30 days:

Procedure	Evaluation	Timing
Diagnostic Imaging	Echocardiography, MUGA or cardiac MRI	Within 30 days after discontinuation if a study has not been performed since last treatment or before the initiation of any non-protocol treatment
Electrocardiogram (ECG)	ECG	Within 30 days after discontinuation
Adverse Events/Toxicity	CTCAE v.4 assessment	Assess Adverse events that were ongoing at the time of discontinuation and record and report any new serious adverse events (up to 30 days after discontinuation)
Response Assessment	Best Response Reason for End of Treatment	Within 30 days after discontinuation
Questionnaires	MOCA, Blessed, FACT-Leu	Within 30 days after discontinuation

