### **8.2 Overall Survival**

Overall survival is measured from the date of registration to death from any cause. Patients not known to have died will be censored on the date they were last known to be alive. Patients will be followed for up to 5 years.

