#### *9.2.2 Definition of a Serious Adverse Event*

A serious adverse event (SAE) is any adverse event that:

Results in death (grade 5)

Is life-threatening

Requires inpatient hospitalization or prolongation of existing hospitalization

Results in persistent or significant disability or incapacity

Is a congenital anomaly/birth defect

These events are to be reported as serious from the start of the infusion on Day 1 to 30 days after completion of the treatment period. Medical and scientific judgment should be exercised in deciding whether expedited reporting is appropriate in other situations such as important medical events that may not be immediately life-threatening or result in death or hospitalization but may jeopardize the patient or may require intervention to prevent one of the events listed above.

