### **11.4 Analysis of Primary Endpoints**

Overall survival will be analyzed using Kaplan-Meier methods. Patients who have not died at the time of analysis will be censored on the date they were last known to be alive. Median survival and the associated 95% confidence interval will be computed using the Brookmeyer-Crowley method. The estimated survival curve will be generated.

Estimates of 30- and 60-day mortality rates will be computed using Kaplan-Meier methods along with associated two-sided 95% confidence intervals computed using the Brookmeyer-Crowley method.

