### **The rights of a research patient to revoke their authorization for use of their PHI:**

In the event that a patient revokes authorization to collect or use PHI, the Investigator, by regulation, retains the ability to use all information collected prior to the revocation of patient authorization. For patients that have revoked authorization to collect or use PHI,

attempts should be made to obtain permission to collect at least vital status (i.e. that the patient is/is not alive) at the end of their scheduled study period.

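### Section 5.2 ends all data collection when a patient asks only to stop treatment; this contradicts 6.3 and 9.2.2 and can leave later deaths out of overall survival

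*Combined protocol and SAP*

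**What the plan says.** Section 5.2 first lists the circumstances in which a patient leaves the Treatment Phase and enters the Follow-up Phase so that efficacy can still be assessed. They include unacceptable toxicity, non-compliance, non-protocol chemotherapy and concurrent illness. The patient's own request is not on that list. It has a separate rule, which applies at every stage: "if a patient requests to stop treatment and/or follow-up, the patient will be discontinued and no further information will be collected". Such a patient is recorded as a withdrawal of consent.

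Other sections treat stopping differently:

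- Section 6.3: "Any patient that completes or discontinues treatment must have the following evaluations performed within 30 days after termination". The evaluations include cardiac imaging, ECG, response, questionnaires, and new SAEs up to 30 days after discontinuation.
- Section 9.2.2: SAEs, which include death, are to be "reported as serious from the start of the infusion on Day 1 to 30 days after completion of the treatment period".
- Section 4.4: patients without a response after up to two inductions "are discontinued from further treatment and followed for survival".
- Section 4.6: "After documentation of persistent leukemia or relapse, follow-up for OS will continue".
- Section 12.7: when a patient revokes authorization to use health information, "attempts should be made to obtain permission to collect at least vital status".

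Overall survival (OS) is the primary efficacy endpoint (11.1.1). Section 8.2 says: "Patients not known to have died will be censored on the date they were last known to be alive". Section 11.4 says: "Patients who have not died at the time of analysis will be censored on the date they were last known to be alive".

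**The concern.** The words and/or in 5.2 place a patient who declines further chemotherapy, but would accept being followed, in the same class as one who refuses all contact. A site cannot follow both 5.2 and 6.3 for that patient. The result is also odd within 5.2 itself: a non-compliant patient is followed for efficacy, while a patient who openly asks to stop treatment is not.

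The main exposure is OS. Such patients are not removed from the analysis; they are censored at the last date known alive. Kaplan-Meier estimation requires that censoring be unrelated to prognosis, and a decision to stop intensive chemotherapy at age 60 or over may well be related to it. If prognosis after stopping is worse, OS reads too long. If it is better, OS reads too short. If it is the same, there is no bias, only lost information. With 30 patients, each lost outcome is 1/30 = 3.3% of the sample. Thirty-day mortality, the primary safety endpoint, could be affected in the same way, but much less.

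**Working it through.** **1. What is collected after each kind of stop**

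| Situation | Section | Afterwards |
|---|---|---|
| No response after up to two inductions | 4.4 | Survival follow-up |
| Persistent leukemia or relapse | 4.6 | OS follow-up continues |
| Toxicity, non-compliance, other chemotherapy, illness | 5.2 list | Follow-up Phase |
| Any discontinuation of treatment | 6.3 | Evaluations, new SAEs to 30 days |
| Death or other SAE | 9.2.2 | Reported to 30 days after the treatment period |
| Health-information authorization revoked | 12.7 | Permission sought for vital status |
| Patient asks to stop treatment only | 5.2 | Nothing |

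Neither 6.3 nor 9.2.2 makes an exception for patient request, so the last row contradicts both.

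**2. The plan's own figure.** Section 11.2 states 80% power with N = 30, median 10 versus 16 months, one-sided 0.05, 24 months of accrual and at least 36 months of follow-up. With exponential survival, uniform accrual and λ = ln 2/median, the probability that a death is observed is 1 − (e^(−36λ) − e^(−60λ))/(24λ). This is 0.960 at median 10 (28.8 deaths) and 0.869 at median 16 (26.1 deaths). Power = Φ(√d × ln 1.6 − 1.645):

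- d = 28.8: Φ(0.88) = 81.0%
- d = 26.1: Φ(0.76) = 77.5%

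A simulated one-sample log-rank test with variance (E+O)/2 gives 80.3%. The stated 80% is reproduced, with no withdrawals assumed.

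**3. Bias in the OS median.** The documents give no withdrawal rate, so all inputs here are assumed. The true median is 10 months (the null value in 11.2). A fraction f is assigned to stop at a time uniform on 0-6 months. The hazard is L before stopping and hL after. L solves

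(1−f)·e^(−10L) + f·e^(−10hL)·(e^(6(h−1)L) − 1)/(6(h−1)L) = 0.5.

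Kaplan-Meier sees only hazard L, so it reads ln 2/L. Example with f = 0.10, h = 2: L = 0.0656, and 0.693/0.0656 = 10.57 months.

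| f | Censored alive, of 30 | h = 0.5 | h = 1 | h = 2 | h = 3 | h = 4 | Shift ÷ 6 months, h = 2 to 4 |
|---|---|---|---|---|---|---|---|
| 5% | 1.2 | 9.80 | 10.00 | 10.28 | 10.45 | 10.57 | 5-10% |
| 10% | 2.5 | 9.60 | 10.00 | 10.57 | 10.94 | 11.20 | 9-20% |
| 20% | 5 | 9.22 | 10.00 | 11.16 | 12.00 | 12.63 | 19-44% |

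A simulation of 1,000,000 patients agrees (for example 11.20 at f = 10%, h = 4). For scale, in samples of 30 with true median 10 and no censoring, the observed median ranges over about 5.5-15.4 months (2.5th to 97.5th percentile).

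**4. Effect on a test of OS.** Section 11.4 names no test, so the one-sample log-rank test of step 2 is assumed.

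- Non-informative stops in months 0-3, true median 16: at 5/10/20% stopping, expected deaths fall from 26.1 to 24.9/23.7/21.3 and power from 80.3% to 78.6/77.1/73.4%.
- Deliberate worst case, each stop one month before death, true median 10: type I error rises from 4.8% to 8.3/13.2/28.2%.

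**5. Thirty-day mortality.** First-induction doses end on day 5 (4.3), and consolidation starts no earlier than 35 days after the last induction course (8.4, note b). A treatment-only request before day 30 can therefore arise mainly on days 1-5 or when a second induction is offered. A death by day 30 in a dosed patient also falls inside the SAE window, so it is lost only if the site follows 5.2 over 6.3 and 9.2.2. If a share u of early deaths went unseen, the probability of more than 3 deaths in the first 15 is P(Bin(15, p(1−u)) ≥ 4):

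| True rate p | u = 0 | u = 2% | u = 5% |
|---|---|---|---|
| 20% | 35.2% | 33.7% | 31.5% |
| 30% | 70.3% | 68.5% | 65.8% |
| 40% | 90.9% | 89.9% | 88.1% |

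**The case against.** The best defense is that 5.2 is the specific rule and 6.3 and 9.2.2 are general ones, so 5.2 may be meant as an exception for withdrawn consent. That is possible, but none of the three sections says so, and 6.3 is worded for any patient. The reading would also still merge refusal of treatment with refusal of follow-up.

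Second, 12.8 lets the health-information authorization sit inside the consent form. Withdrawing consent might then also revoke the authorization and bring the vital-status step of 12.7 into play. The consent pages were not available and may already separate the two requests, and 5.2 does not forbid asking. All of this could reduce the practical loss. It does not reconcile the protocol text.

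Third, the magnitude rests on assumed inputs, and treatment-only requests may be few. Consolidation is at the investigator's choice, second induction is limited to some patients, and most other reasons for stopping lead to follow-up. Patients who refuse all follow-up would be recovered only if they permit vital status to be collected. This stands: the 20% rows and the worst case in step 4 show the mechanism and are not forecasts.

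Fourth, the analyses are mainly descriptive and 11.4 names no OS test, so a shift in the median is not tied to a decision rule. That limits the consequence, but the estimate itself would still be affected.

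Finally, 5.2 also says that certain adverse events lead to discontinuation from the study, although its own list sends unacceptable toxicity to follow-up. That is a further inconsistency to reconcile in the same section.

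**Conclusion.** The concern holds. On its wording, 5.2 stops all data collection after a treatment-only request. That contradicts 6.3 directly and 9.2.2 by the absence of any exception, and it leaves deaths after the SAE window with no stated route into the primary efficacy endpoint.

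The direction and size of the bias cannot be known from the documents. They depend on three things not given: how many patients make such a request, when, and how their prognosis then differs. Under the assumptions shown, the effect on the median runs from a fall of 0.8 months (20% stopping, half the hazard), through none at equal hazard, to rises of 0.6-1.2 months (10% stopping) and 1.2-2.6 months (20% stopping) at two to four times the hazard. All are smaller than sampling error at N = 30, but they do not average out. The effect on 30-day mortality and on the early stopping rule is small. The 80% power figure in 11.2 is not itself in error. The change should be made because the contradiction is clear, the remedy is cheap, and vital status that was never collected may not be recoverable later.

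**What to change.** Reword 5.2 to separate the two requests:

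- A patient who asks only to stop treatment stays in follow-up, at least for survival status, with the safety evaluations and reporting of 6.3 and 9.2.2.
- Only an explicit refusal of follow-up is classed as withdrawal of consent. Permission to collect vital status is then sought, as 12.7 already does for revoked authorization.
- The case report form records which request was made and its date.

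Align the consent form if it differs, and state in 5.2 whether patients discontinued from the study for adverse events remain in survival follow-up. None of this alters when treatment stops.

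The cost is protocol wording, possibly consent wording, and survival contacts for the few patients concerned: at most 12 monthly contacts in year 1, then date of death or alive at Year 5 (6.4), with at least annual contact for those alive and in remission (4.6). Other follow-up tests would be added only if the patient agrees. The sample size does not change.

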## 6 Treatment of Patients

See APPENDIX 1: Patient Evaluation Flow Sheet

### 6.1 Pre-Treatment Evaluations

After providing informed consent, eligible patients are registered to the study.

The date of the first test or exam will be considered as the date of the screening visit.

Procedure	Evaluation	Timing
Informed Consent	
It should be personally signed and dated by the patient. The responsible investigator must also personally sign and date the document.
 
A copy of the Informed Consent must be given to the patient.
 
The patient's study screening must be conspicuously noted in the source documentation.
	Informed consent should be obtained prior to initiation of screening procedures. If the period between ICF signature date and induction 1, day 1 visit is $\geq 30$ days the patient must sign another ICF.
Demography	Date of birth, sex, race, ethnicity	Within 14 days prior to Registration
Medical History	
Complete medical history
 
 
• Resolved conditions
 
• Intermittent conditions
 
• Concurrent illnesses
 
• Previous surgeries
 
	Within 14 days prior to registration
Leukemia History	
Leukemia, MDS, and MPN History
 
Prior chemotherapies
 
Prior leukemia treatment
	Within 14 days prior to registration
Physical Exam	
Objective review of body systems
 
Height
 
Weight
 
BSA
 
ECOG Performance Status
	Within 3 days prior to registration
Vital Signs	
Heart rate
 
Blood pressure
 
Temperature
 
Respiratory rate
	Within 3 days prior to registration
Hematology	
Hemoglobin
 
White Blood Count
 
Platelets
 
Differential Count
	Within 1 day prior to registration
Biochemistry	
BUN
 
Creatinine
 
Uric Acid
 
Electrolytes (Sodium, Potassium, Chloride)
 
Bilirubin
 
Alkaline phosphatase
 
AST or ALT
 
LDH
 
Protein
 
Calcium
 
Albumin
 
Glucose
	Within 1 day prior to registration
Urinalysis	
pH
 
specific gravity
 
glucose
 
protein
 
ketones
 
blood
	Within 3 days prior to registration
Questionnaires	MOCA, Blessed, FACT-Leu	Within 7 days prior to registration

Procedure	Evaluation	Timing
Bone Marrow Aspiration/Biopsy	Morphology	Within 14 days prior to registration
Diagnostic Imaging	Chest X-ray or Chest CT	Within 28 days prior to registration
Diagnostic Imaging	Echocardiography, MUGA or cardiac MRI scan	Within 14 days prior to registration
Electrocardiogram (ECG)	ECG	Within 14 days prior to registration
Cytogenetics	Cytogenetics (performed locally)	Within 3 months prior to registration
Molecular Studies	Central or local laboratory evaluation of CEBPA, FLT3, and NPM1 (either PB or BM)	Within 3 months prior to registration

## 6.2 Evaluation during Treatment Phase

Inductions and consolidations are administered as courses. A course consists of the administration of therapy with scheduled assessments to evaluate the response to treatment. The first induction may end before the completion of all evaluations if a second induction is necessary, (see Section 4.4). Induction is completed when a patient has

- A confirmed CR (see section 8.4)
- A CRp or CRi (see section 8.4) and is to begin consolidation treatment before hematologic count recovery
- Persistent/recurrent disease (PD/relapse)
- Response evaluation cannot be performed because of the patient's condition and no further study treatment can or will be administered.

Patients with a CR or CRi may receive up to 2 consolidation treatments.

Procedure	Evaluation	Timing
Physical Exam	Objective review of body systems Weight BSA	Days 14 and 42
Vital Signs	Heart rate Blood pressure Temperature Respiratory rate	Days 14 and 42
Hematology	Hemoglobin White Blood Count Platelets Differential Count	Days 1, 3, 5, 7±3, 10±1, 14±2, then weekly (±2days) until whichever occurs last: - Day 42 - peripheral blood count recovery - removed from Treatment Phase

Procedure	Evaluation	Timing
Biochemistry	BUN Creatinine Uric Acid Electrolytes (Sodium, Potassium, Chloride) Bilirubin Alkaline phosphatase AST or ALT LDH Protein Calcium Albumin Glucose	Days 1, 3, 5, 7±3, 10±1, 14±2, then weekly (±2days) until whichever occurs last: - Day 42 - peripheral blood count recovery - removed from Treatment Phase
Bone Marrow Evaluation	Morphology	As needed to confirm response or determine antileukemic effect and need for second induction.
Cytogenetics Molecular Studies	Cytogenetics Molecular Studies	Required in patients with a CR, CRp, or CRI with positive baseline findings (perform at the time of bone marrow assessment for CR or CRI). Optional in patients with normal baseline cytogenetics/molecular studies.
Diagnostic Imaging	Echocardiography, MUGA or cardiac MRI scan	After the last induction and before each consolidation cycle.
Questionnaires	MOCA, Blessed, FACT-Leu	Days 7±3, 42±3, Induction 2 Day 1(±3)
Adverse Events/Toxicity	CTCAE v.4 assessment	Continual assessment starting from the first dose until 30 days after completion of the Treatment Period.
Concomitant Medications		Continual assessment during Treatment Period.

### 6.3 Early Termination or End of Treatment Phase

Any patient that completes or discontinues treatment must have the following evaluations performed within 30 days after termination and prior to the initiation of any salvage therapy, if not performed within the last 30 days:

Procedure	Evaluation	Timing
Diagnostic Imaging	Echocardiography, MUGA or cardiac MRI	Within 30 days after discontinuation if a study has not been performed since last treatment or before the initiation of any non-protocol treatment
Electrocardiogram (ECG)	ECG	Within 30 days after discontinuation
Adverse Events/Toxicity	CTCAE v.4 assessment	Assess Adverse events that were ongoing at the time of discontinuation and record and report any new serious adverse events (up to 30 days after discontinuation)
Response Assessment	Best Response Reason for End of Treatment	Within 30 days after discontinuation
Questionnaires	MOCA, Blessed, FACT-Leu	Within 30 days after discontinuation

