**Safety Variables & Analysis:**

Patients will be monitored for all clinical adverse events as well as laboratory evaluations.

- Induction Mortality: assessed at Day 30 and 60; therapies may be changed after 30 days.
- Serious Adverse Events
- Adverse Events: Grades 1-5 and Grades 3-5
- Laboratory Evaluations
  - Routine hematology (CBC+diff+Platelet count) and chemistry (with LDH)
  - Time to hematologic recovery and proportion with prolonged cytopenias ( $\geq$  56 days)
- Cardiac Evaluations
  - Cardiac AEs: Grades 1-5 and Grades 3-5
  - ECG changes (pre-dose for each course, and at the end of each course)
  - LVEF changes (pre and post treatment)

---

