**Other Variables & Analysis:**

**Quality of Life Assessment:** FACT-Leu will be used to assess patients at the start of treatment and one month after treatment completion.

---

**Cognitive Assessment:** The Blessed Orientation-Memory-Concentration Test and the Montreal Cognitive Assessment Mini will be administered at the start of treatment and one month after completion of therapy.

**Cardiac Assessments:** All ECG and ECHO/cardiac MRI assessments will be obtained and read locally for patient care.

---

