Day 150 or 45 Days after the last treatment whichever is later

See Section 9.3, Repeat ECHO/MUGA/cardiac MRI before the second consolidation

ECG will be performed pre-dose for each course of treatment, and at the end of each course or EOT.

Blessed, MOCA and FACT-Leu can be administered +/- 3 days from indicated day

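### The 30-day look-back in section 6.3 lets a Day 7 or Induction 2 Day 1 questionnaire set replace the end-of-treatment FACT-Leu, MoCA and Blessed in patients who stop early

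*Combined protocol and SAP*

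**What the plan says.** The lead sentence of section 6.3 requires the listed evaluations to be "performed within 30 days after termination and prior to the initiation of any salvage therapy, if not performed within the last 30 days". The questionnaire row (MoCA, Blessed, FACT-Leu) adds only that they fall in the 30 days following discontinuation.

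During treatment, section 6.2 schedules the questionnaires at "Days 7±3, 42±3, Induction 2 Day 1(±3" days). Section 6.4 and Appendix 2, which govern follow-up, list none.

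The synopsis, under Other Variables & Analysis, states that "FACT-Leu will be used to assess patients at the start of treatment and one month after treatment completion", and gives the two cognitive tests the same timing. Quality of life by FACT-Leu is a secondary objective in the synopsis and in section 3.2.

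Two other rows of the 6.3 table need comparing with the lead sentence:

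- **Imaging.** The row has its own condition: the scan is due "if a study has not been performed since last treatment". Section 6.2 also schedules imaging "After the last induction and before each consolidation cycle".
- **ECG.** The row has no such condition, but Appendix 1 footnote 8 says "ECG will be performed pre-dose for each course of treatment, and at the end of each course or EOT", and the synopsis safety variables also include an ECG at the end of each course.

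**The concern.** A look-back is normally there to spare a patient a repeat of something just done. It does that only if the earlier assessment measures the same state. Here the reference point is termination, so an assessment made in the dosing week, or before the final course has finished, is accepted as the end-of-treatment value.

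The patients exposed are those who leave the Treatment Phase early. Section 5.2 lists persistent disease and unacceptable toxicity among the reasons. These patients may well differ in quality of life from those who stay to the Day 42 visit. If their post-treatment value is missing, or is really a Day 7 value, a start-to-end comparison in 30 patients rests mainly on those who remained. Section 11 has no FACT-Leu change analysis and no missing-data rule that would flag a substituted value.

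**Working it through.** The plan states no figure to reproduce; this is date arithmetic on its own windows. Day 1 is the first dose.

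**Inputs**

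- Look-back: 30 days (6.3), read as counted back from termination.
- First induction dosed on Days 1, 3 and 5; second induction on Days 1 and 3 (4.3, 4.4, 7).
- Questionnaires at Day 7±3 (Day 4 to 10), Day 42±3 (Day 39 to 45) and Induction 2 Day 1±3 (6.2).
- A non-evaluable or equivocal Day 14 marrow may be repeated 5 to 14 days later (Appendix 1 footnote 5), that is on Day 19 to 28.

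**Formula.** Last stopping day for which a set triggers the waiver = day of the set + 30.

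**Day 7 set, first induction**

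- Done Day 4: 4 + 30 = Day 34.
- Done Day 7: 7 + 30 = Day 37.
- Done Day 10: 10 + 30 = Day 40.

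Relative to the Day 5 dose, the set falls between 4 − 5 = −1 and 10 − 5 = +5 days. Thirty days after that dose is Day 35.

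**Worked case.** A patient is declared to have persistent disease and stops on Day 28. The Day 7 set is then 28 − 10 = 18 to 28 − 4 = 24 days old, inside the look-back, so 6.3 asks for no end-of-treatment set. The Day 42 window opens 39 − 28 = 11 days after the patient has left the Treatment Phase. Follow-up adds none.

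**Induction 2 Day 1 set**

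- On the nominal day: 1 + 30 = Induction 2 Day 31.
- Across the ±3 window: Induction 2 Day 28 to 34.

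On the nominal day this set is 3 − 1 = 2 days before the last dose of that course, so it cannot describe the patient after it.

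**Where the look-back does no harm.** A Day 42 set falls 39 − 5 = 34 to 45 − 5 = 40 days after the Day 5 dose. That is close to the synopsis timing, so letting it stand for a one-induction patient who stops later is reasonable. The problem is confined to sets taken in or near a dosing week.

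**Would tying the waiver to the last dose suffice?** No. A set on Day 6 to 10 already follows the Day 5 dose by 1 to 5 days and would still qualify, although it is far from one month.

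The column positions of the questionnaire marks in the Appendix 1 grid cannot be read reliably, so nothing above rests on them.

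**The case against.** The synopsis is part of the same document and asks for the one-month assessment. Section 6.3 permits a site to skip the set; it does not forbid following the synopsis. That is fair: the defect is a conflict between two rules. But 6.3 is the operative visit table, and a site that follows it exactly commits no deviation by skipping the set.

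It can also be said that a Day 6 to 10 set follows the last first-induction dose and so is not pre-treatment. This stands, and it means the value is mistimed rather than wholly uninformative.

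The importance should not be overstated. The analyses are mainly descriptive (section 11), the cognitive objective is the relation of cognition to outcome, and that analysis is labelled hypothesis generating (11.2). The stake is chiefly the FACT-Leu objective.

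Four stronger readings are tempting, and the documents do not support them:

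- **LVEF could go unmeasured after treatment.** The imaging row's own test cannot be met by a baseline or pre-course scan, and 6.2 adds a scan after the last induction. The lead sentence and the row disagree in wording, and the row's closing clause about non-protocol treatment is unclear, but the scan is still required.
- **ECG could go unmeasured.** Footnote 8 and the synopsis require a trace at the end of the course or of treatment, with no look-back.
- **Everyone who leaves before Day 42 is exempted.** A Day 4 set covers stopping only through Day 34 and a Day 7 set through Day 37, while the next window opens on Day 39.
- **The screening value routinely stands in.** By date alone it could: a set taken up to 7 + 3 = 10 days before Day 1 covers stopping through Day 21, and one taken on Day 1 through Day 31. But once the Day 7 window has closed, this needs that set to have been missed, which is a protocol deviation.

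**Conclusion.** The point holds for the questionnaires. Followed as written, 6.3 drops the end-of-treatment FACT-Leu, MoCA and Blessed for a first-induction patient who stops up to Day 34 to 40 with a Day 7 set on file, and for a second-induction patient who stops up to about Induction 2 Day 31 with a Day 1 set on file. This contradicts the synopsis, and no later visit recovers the value.

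It rests on two readings: that the look-back counts from termination, and that a discontinued patient no longer attends Treatment Phase visits, as 5.2 implies. That the loss is not random is a judgement from the listed reasons for stopping; the documents do not quantify it.

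A reader might try to derive a patient count from the phase 3 response and mortality rates in section 2.4. That would need an assumed fraction of non-responders who stop before Day 42, and second inductions, allowed up to 60 days, shift when they leave. The documents give no early-discontinuation rate, so no count is offered.

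For imaging and ECG there are wording conflicts to reconcile, not missing endpoints.

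**What to change.** In 6.3, exempt the questionnaires from the look-back. Time them at about one month after the last dose of study drug, with a stated window, or earlier if non-protocol therapy is about to start. Record the date of each set relative to the last dose. State in the synopsis whether treatment completion means the last dose or the end of the Treatment Phase, and use the same timing in Appendix 1. If the window extends to 40 days after the last dose, the Day 42 set of a one-induction patient counts and no duplicate is needed.

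Separately, reword the 6.3 lead sentence so that it agrees with its own imaging row and with the end-of-course or end-of-treatment ECG in the synopsis and Appendix 1 footnote 8, and clarify the closing clause of the imaging row.

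The cost is a short amendment and one questionnaire session for some early leavers. The imaging and ECG wording adds no assessment that the documents do not already require.
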